7.1.3.2. Determination of Overall Response by Choi Criteria

Central radiographic review will separately assess overall response using Choi criteria [66], as summarized in Table 14. The overall assessment of response will involve all parameters as depicted in Table 20 below.

Table 20: Choi Response Criteria

Response	Definition
CR	Disappearance of all lesions
	No new lesions
PR	A decrease in size $\geq 10\%$ or a decrease in tumor attenuation (Hounsfield units) $\geq 15\%$ on CT
	No new lesions
	No obvious progression of non-measurable disease
SD	Does not meet criteria for CR, PR or PD
	No symptomatic deterioration attributed to tumor progression
PD	An increase in tumor size $\geq 10\%$ and does not meet criteria of PR by tumor attenuation on CT
	New lesions

7.1.4. Central Review of Disease Assessments

Central review of imaging studies and clinical information documenting disease status will be performed retrospectively to verify disease response and progression during study. It is important to the integrity of the study that all imaging studies and clinical information (including photographs) are forwarded to the review laboratory as each patient enrolls and progresses through the study.

Materials to be forwarded for central review are the following:

1. All imaging studies performed on study, preferably in digital format on compact disc or optical disc. All digital media must be in DICOM format. Films may be forwarded for review if

necessary; all films must be originals (second original films acceptable) rather than copies of films.

2. Photographs of sites of disease assessed using clinical methods. Details concerning clinically assessed lesions will be collected on the CRFs and made available to the core laboratory.

Further information on materials to be forwarded for central review is provided in the Regulatory Binder.

8. ASSESSMENT OF SAFETY

8.1. Safety Parameters

Safety will be characterized in terms of the incidence, timing, severity (graded by the National Cancer Institute [NCI] Common Terminology Criteria for Adverse Events [CTCAE], Version 4.0), seriousness, and relatedness of adverse events and laboratory abnormalities. In addition, physical examination, vital signs, and ECOG performance status will be serially monitored. Laboratory safety analyses will be based on the local laboratory data, and will include hematology, serum chemistry (including liver and kidney function), urinalysis, serum or urine pregnancy testing, and coagulation profile. Serum will also be assessed for immunogenicity to TRC105 (APA titers). In addition, ECGs will be recorded at baseline and day 1 of each cycle and as clinically indicated throughout the study.

8.1.1. Laboratory Safety Assessments

Abnormal and clinically significant laboratory tests should be recorded as adverse events. To meet the definition of clinically significant, the test result generally requires a change in medical management (e.g. new medication, unplanned treatment, additional tests, etc.).

8.1.1.1. Hematology, Serum Chemistry, Coagulation, Pregnancy Test

Assessments will be performed at the time points indicated in the Schedule of Assessments ([Table 7](#), [Table 8](#), [Table 9](#), [Table 10](#), and [Table 11](#)) and analyzed at local laboratories.

Investigators may have additional blood tests performed for the purpose of planning treatment administration, or for following adverse events as clinically indicated.

- Hematology: CBC with differential and platelet count. Iron studies (serum iron, ferritin and total iron binding capacity).
- Coagulation: International Normalized Ratio (INR) will be assessed
- Serum Chemistry: Total bilirubin, alanine transaminase (ALT), aspartate transaminase (AST), alkaline phosphatase, lipase, amylase, total protein, albumin, sodium, potassium, bicarbonate, chloride, calcium, phosphorus, blood urea nitrogen, creatinine, thyroid stimulating hormone and glucose
- Pregnancy test: Serum or urine pregnancy tests will be performed locally on all female patients of childbearing potential.

8.1.1.2. Urinalysis

Urinalysis (without microscopic analysis, unless indicated) will be performed at time points indicated in the Schedule of Assessments (see [Table 7](#), [Table 8](#), [Table 9](#), [Table 10](#), and [Table 11](#)) and analyzed by local laboratories. Microscopic analysis and/or urine protein-creatinine ratio (UPCR) should be performed as clinically indicated.

8.1.1.3. Physical Examination

A physical examination including, but not limited to, general appearance, head, eyes, ears, nose, throat, neck, heart, chest, abdomen, musculoskeletal, extremities, skin, lymph nodes, neurological genitourinary (as appropriate), and rectal (as appropriate) will be assessed at timepoints indicated within the Schedule of Assessments (see [Table 7](#), [Table 8](#), [Table 9](#), [Table 10](#), and [Table 11](#)). The physical examination will include examination of known and suspected sites of disease.

8.1.1.4. Vital Signs

Heart rate, temperature, blood pressure, respiratory rate and weight will be assessed at timepoints indicated within the Schedule of Assessments (see [Table 7](#), [Table 8](#), [Table 9](#), [Table 10](#), and [Table 11](#)). Heart rate, temperature, blood pressure, and respiratory rate will also be assessed during TRC105 infusions as described in [Section 4.1.2.2](#) and the footnotes of the Schedule of Assessments.

8.1.1.5. Performance Status

The ECOG scale will be used to assess performance status at Screening.

8.1.1.6. ECG

A single 12-lead (with a 10-second rhythm strip) tracing will be used for all ECGs. It is preferable that the machine used has a capacity to calculate standard intervals automatically. ECG will be performed at the time-points indicated in the Schedule of Assessments (see [Table 7](#), [Table 8](#), [Table 9](#), [Table 10](#), and [Table 11](#)) and as clinically indicated throughout the study

8.2. Adverse Events

All observed or volunteered adverse events regardless of suspected causal relationship to TRC105 study drug will be reported as described below.

8.2.1. Definition of Adverse Event

An adverse event is any untoward medical occurrence in a trial patient who is administered a drug or biologic (medicinal product); the event may or may not have a causal relationship with the medicinal product. Examples of adverse events include, but are not limited to the following:

- Clinically significant symptoms and signs including:
 - Worsening of signs and symptoms of the malignancy under trial (disease progression without worsening of signs and symptoms assessed by measurement of malignant lesions on radiographs or other methods should not be reported as adverse events).
 - Signs and symptoms resulting from drug overdose, abuse, misuse, withdrawal, sensitivity, dependency, interaction or toxicity.
 - All possibly related and unrelated illnesses, including the worsening of a preexisting illness.

-
- Injury or accidents. Note that if a medical condition is known to have caused the injury or accident (hip fracture from a fall secondary to dizziness), the medical condition (dizziness) and the outcome of the accident (hip fracture from a fall) should be reported as 2 separate adverse events.
 - Symptoms or signs resulting from exposure *in utero*.
 - Abnormalities in physiological testing or physical examination findings that require clinical intervention or further investigation (beyond ordering a repeat confirmatory test).
 - Laboratory abnormalities that meet any of the following (Note: merely repeating an abnormal test, in the absence of any of the below conditions, does not constitute an adverse event. Any abnormal test result that is determined to be an error does not require reporting as an adverse event.):
 - Test result that is associated with accompanying symptoms
 - Test result that requires additional diagnostic testing or medical/surgical intervention
 - Test result that leads to a change in TRC105 study drug dosing not stipulated in the protocol or discontinuation from the trial, significant additional concomitant drug treatment, or other therapy
 - Test result that is considered to be an adverse event by the Investigator or TRACON

8.2.2. Serious Adverse Events

An adverse event that meets one or more of the following criteria/outcomes is classified as serious:

- Results in death
- Is life-threatening (i.e., at immediate risk of death)
- Requires in patient hospitalization or prolongation of existing hospitalization
- Results in persistent or significant disability/incapacity
- Results in congenital anomaly/birth defect
- Other important medical events that may not result in death, be life-threatening, or require hospitalization may be considered serious when, based upon appropriate medical judgment, they may jeopardize the patient or may require medical or surgical intervention to prevent one of the outcomes listed above. Examples of such events are intensive treatment in an emergency room for allergic bronchospasm; blood dyscrasias or convulsions that do not result in hospitalization; or the development of drug dependence or drug abuse.
- Cases of potential drug-induced liver injury as assessed by laboratory test values (“Hy’s Law Cases”) are also reportable as an SAE. If a Study subject develops abnormal values (3 x ULN) in aspartate transaminase (AST) or alanine transaminase

or both, concurrent with abnormal elevations (2 x ULN) in total bilirubin and no other known cause of liver injury, that event would be classified as a Hy's Law Case and an SAE.

Serious also includes any other event that the Investigator or sponsor judges to be serious, or which is defined as serious by the HRA in the country in which the event occurred.

Progression of the malignancy under study (including signs and symptoms of progression) should not be reported as SAEs unless the outcome is fatal during the trial or within the safety reporting period. Hospitalizations due to signs and symptoms of disease progression should not be reported as SAEs. If the malignancy has a fatal outcome during the trial or within the safety reporting period, then the event leading to death must be recorded as an adverse event and as an SAE with CTC grade 5.

The onset date of an SAE is defined as the date on which the event initially met serious criteria (e.g., the date of admission to a hospital). The end date is the date on which the event no longer met serious criteria (e.g., the date the patient was discharged from a hospital).

8.2.2.1. Hospitalization

Adverse events associated with in-patient hospitalization, or prolongation of an existing hospitalization, are considered serious. Any initial admission, even if the duration is less than 24 hours is considered serious. In addition, any transfer within the hospital to an acute/intensive care unit is considered serious (e.g., transfer from the psychiatric wing to a medical floor or transfer from a medical floor to a coronary care unit). However, the following hospitalizations **should not** be considered serious:

- Rehabilitation facility admission
- Hospice facility admission
- Respite care
- Skilled nursing facility admission
- Nursing home admission
- Emergency room visit
- Outpatient same day surgery/procedure
- Hospitalization or prolongation of hospitalization in the absence of precipitating clinical adverse events as follows:
 - Admission for treatment of preexisting condition not associated with the development of a new adverse event or with a worsening of the preexisting condition
 - Social admission
 - Administrative admission (e.g. for yearly physical exam)
 - Protocol-specified admission during a clinical trial

-
- Optional admission not associated with a precipitating clinical adverse event (e.g. for elective cosmetic surgery)
 - Preplanned treatments or surgical procedures that are not related to an SAE
 - Hospitalization for observation without an AE
 - Diagnostic and therapeutic noninvasive and invasive procedures, such as surgery, should not be reported as adverse events. The medical condition for which the procedure was performed should be reported if it meets the definition of an adverse event (e.g. acute appendicitis that begins during the adverse event reporting period should be reported as an adverse event and the appendectomy should be recorded as a concomitant treatment).

8.3. Reporting Adverse Events

8.3.1. Eliciting Adverse Event Information

The Investigator is to report all directly observed adverse events and all adverse events spontaneously reported by the trial patient using concise medical terminology. In addition, each trial patient will be questioned about adverse events at each clinic visit following initiation of treatment. The question asked will be, "Since your last clinic visit have you had any health problems?"

8.3.2. Adverse Event Reporting Period

Safety information for each patient will be collected from the date of informed consent. Adverse events occurring prior to the initiation of the study treatment will be considered "baseline-emergent adverse events" and will be recorded on corresponding case report forms and will not be retained for patients who fail screening. The adverse event reporting period for this trial begins when the patient has taken the first dose of axitinib or TRC105 study drug and ends 28 days after the last dose of axitinib or TRC105 study drug is administered.

All adverse events that occur in trial patients during the adverse event reporting period specified in the protocol must be reported to TRACON, whether or not the event is considered study treatment-related. In addition, any known untoward event that occurs beyond the adverse event reporting period that the Investigator assesses as possibly related to the investigational medication/product should also be reported as an adverse event.

Serious adverse events that are unexpected and associated with use of the study medication will be reported to the US Food and Drug Administration (FDA), Competent Authorities and Ethics Committees in other countries taking part in the study, as well as all participating clinical sites in all countries. Investigators should report to their local IEC/IRB as dictated by their board's policies and procedures. For events which are fatal or life-threatening, unexpected, and associated with use of the investigational product, a 7-Day Alert Report will be submitted to the regulatory authorities within 7 calendar days of receipt of the SAE information. For all other events that are serious, unexpected, and associated with use of the investigational product, a written report will be made no more than 15 calendar days from the date TRACON learns of the event. Participating clinical sites will be notified of these events in parallel.

All adverse events, including SAEs, are to be reported on the adverse event CRFs.

8.3.4. Recording Adverse Events in the Case Report Forms

The Investigator is to report all directly observed adverse events and all adverse events spontaneously reported by the trial patient. In addition, each trial patient will be questioned about adverse events. All adverse events that meet the criteria specified in [Section 8.2.1](#) are to be recorded on patient source documents and on the CRFs. Adverse events should be reported using concise medical terminology on the CRFs.

8.3.5. Grading of Adverse Event Severity

To report adverse events on the CRFs, the Investigator will use the severity grading as described in NCI CTCAE (Version 4.0).

Every effort should be made by the Investigator to assess the adverse event according to CTCAE criteria. If the Investigator is unable to assess severity because the term is not described in NCI (Version 4.0), severity of MILD, MODERATE, SEVERE, LIFE-THREATENING, or FATAL may be used to describe the maximum intensity of the adverse event. For purposes of consistency, these intensity grades are defined as follows:

Table 21: Adverse Event Grading

Grade	Non-CTCAE Severity	Definition
1	Mild	Does not interfere with patient's usual function
2	Moderate	Interferes to some extent with patient's usual function
3	Severe	Interferes significantly with patient's usual function
4	Life-Threatening	Results in immediate risk of patient's death
5	Fatal	Results in patient's death

Note the distinction between the severity and the seriousness of an adverse event. A severe event is not necessarily a serious event. For example, a headache may be severe (interferes significantly with patient's usual function) but would not be classified as serious unless it met one of the criteria for serious events.

8.3.6. Relationship to TRC105 Study Drug/Axitinib

In this study, TRC105 study drug is given in combination with Axitinib. The relationship of an adverse event to TRC105 study drug and axitinib should be classified by the Investigator using the following guidelines:

- Suspected Adverse Reaction to TRC105 (Arm B only): There is a reasonable possibility that TRC105 caused the adverse event (i.e., there is evidence to suggest a causal relationship between TRC105 and the adverse event).
- Suspected Adverse Reaction to axitinib (Arm A or B): There is a reasonable possibility that axitinib caused the adverse event (i.e., there is evidence to suggest a causal relationship between axitinib and the adverse event)

-
- Not Related: There is no reasonable possibility that the adverse event is associated with TRC105 study drug or axitinib.

AE's maybe related to both drugs. AE's related to TRC105 study drug or Axitinib are considered Adverse Drug Reactions (ADR).

8.3.7. Expectedness

All TRC105 adverse events and adverse drug reactions are considered "unexpected" if it's not listed in the investigator brochure or not listed at the specificity or severity that has been observed. For example, under this definition, hepatic necrosis would be unexpected (by virtue of greater severity) if the investigator brochure referred only to elevated hepatic enzymes or hepatitis. Similarly, cerebral thromboembolism and cerebral vasculitis would be unexpected (by virtue of greater specificity) if the investigator brochure listed only cerebral vascular accidents. "Unexpected," as used in this definition, also refers to adverse events or suspected adverse reactions that are mentioned in the investigator brochure as occurring with a class of drugs or as anticipated from the pharmacological properties of the drug, but are not specifically mentioned as occurring with the particular drug under investigation.

All axitinib adverse events and adverse drug reactions are considered "unexpected" if it's not listed in the package insert or not listed at the specificity or severity that has been observed. "Unexpected," as used in this definition, also refers to adverse events or suspected adverse reactions that are mentioned in the package insert as occurring with a class of drugs or as anticipated from the pharmacological properties of the drug, but are not specifically mentioned as occurring with axitinib.

8.3.8. Exposure *in Utero*

A pregnant patient will be withdrawn from the study. If any trial patient (or partner of a trial patient) becomes or is found to be pregnant during the study or within 180 days of discontinuing TRC105 or axitinib, the Investigator must report the information to TRACON, or designee via the Pregnancy Notification Report Form. This must be done irrespective of whether an adverse event has occurred and within 24 hours of awareness of the pregnancy. The information submitted should include the anticipated date of delivery.

The Investigator will follow the patient until completion of the pregnancy or until pregnancy termination (i.e., induced abortion) and then notify TRACON, or its designee, of the outcome within 5 days or as specified below. The Investigator will provide this information as a follow-up to the initial report. The reason(s) for an induced abortion must be specified.

For pregnancies of partners of male participating in the study: all partners who become pregnant and provide appropriate consent to TRACON will be monitored to the completion or termination of the pregnancy as described above.

The Investigator should follow procedures for reporting an SAE if pregnancy outcome meets criteria for an SAE (i.e., spontaneous abortion, stillbirth, neonatal death, or congenital anomaly [including that in an aborted fetus]).

In the case of a live birth, the “normality” of the newborn can be assessed at the time of birth and the Pregnancy Outcome Report Form should be completed (i.e., no minimum follow-up period of a presumably normal infant must pass before a Pregnancy Outcome Report Form can be completed). The “normality” of an aborted fetus can be assessed by gross visual inspection unless pre-abortion laboratory findings are suggestive of a congenital anomaly.

Additional information about pregnancy outcomes that are classified as SAEs follows:

- “Spontaneous abortion” includes miscarriage and missed abortion.
- All neonatal deaths that occur within 1 month of birth should be reported, without regard to causality, as SAEs. In addition, any infant death after 1 month that the Investigator assesses as possibly related to the *in utero* exposure to the investigational medication should also be reported.

8.3.9. Follow-up of Unresolved Adverse Events

All adverse events should be followed until they are resolved or the Investigator assesses them as chronic or stable. Any increase or decrease in adverse event grade should be recorded as a new adverse event.

All serious and those non-serious events assessed by the Investigator as possibly related to the investigational medication/product should continue to be followed even after the patient’s participation in the trial is over. Such events should be followed until they resolve or until the Investigator assesses them as “chronic” or “stable.” The event should also be documented on the adverse event CRF.

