5. SELECTION AND WITHDRAWAL OF PATIENTS

5.1. Patient Inclusion Criteria

5.1.1. Inclusion Criteria:

1. **PHASE 2 ONLY:** Histologically confirmed advanced or metastatic renal cell carcinoma with a clear cell component that has progressed by investigator assessment on treatment with one and only one multi-targeted tyrosine kinase inhibitor (TKI) other than axitinib that targets the VEGF receptor (VEGFR) (e.g., sunitinib, pazopanib, sorafenib, tivozanib, cabozantinib) **OR** bevacizumab. Patients who received VEGF inhibitor treatment for < one month due to documented intolerance in the absence of progression, and were started on a second VEGF inhibitor within one month of discontinuing the initial VEGF inhibitor are eligible. One prior immunotherapy (interleukin-2 or interferon-alpha or immune checkpoint inhibitor or tumor vaccine) and one prior mTOR inhibitor treatment are allowed. Prior adjuvant therapy is permitted in the absence of disease progression during treatment, but no further VEGF treatment is allowed if progression occurred on adjuvant VEGF inhibitor treatment.
2. **PHASE 1B COHORT 3 AND 4 ONLY:** Histologically confirmed advanced or metastatic renal cell carcinoma that has progressed by investigator assessment on treatment with at least **TWO** VEGF inhibitors (e.g., sunitinib, pazopanib, sorafenib, tivozanib, cabozantinib, bevacizumab). Prior immunotherapy (interleukin-2 or interferon-alpha or immune checkpoint inhibitor or tumor vaccine), or mTOR inhibitor treatment is allowed.
3. No other prior malignancy is allowed except for the following: adequately treated basal cell or squamous cell skin cancer, adequately treated Stage I or II cancer from which the patient is currently in complete remission per investigators' clinical judgment.
4. Measurable disease by RECIST 1.1 criteria
5. Age of 18 years or older
6. ECOG performance status ≤ 1
7. Resolution of all acute adverse events resulting from prior cancer therapies to NCI CTCAE grade ≤ 1 or baseline (except alopecia)
8. Adequate organ function as defined by the following criteria:
 - AST and ALT $\leq 2.5 \times$ ULN **OR** $\leq 5 \times$ ULN in cases of liver metastases
 - Total serum bilirubin ≤ 1.5 times the upper limit of normal
 - Absolute neutrophil count (ANC) $\geq 1500/\mu\text{L}$
 - Platelets $\geq 100,000/\mu\text{L}$ without transfusion support within the past 28 days

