12.2. Adverse Events

All AEs with an onset after initiation of treatment will be considered as treatment-emergent AEs. A preexisting condition that worsens during the treatment period will also be considered as a treatment emergent AE. All AEs will be coded by system organ class (SOC) and preferred term using NCI CTCAE (MedDRA) version 4.0.

The number and percentage of patients with the following types of treatment-emergent AEs will be summarized for each study arm: common and serious AEs, AEs related to study medication, AEs resulting in study discontinuation, and clinically significant laboratory abnormalities. Laboratory data will be summarized for baseline, treatment visits and change from baseline as appropriate for each arm. Non-treatment-emergent serious AEs will be described separately. Deaths will be reported with demographic information. Comparison of categorical values will be made by Chi-square or Fisher exact test and of continuous variables will be made by Student t test.

For the phase 1b portion treatment-emergent AEs will be summarized by dose level. For the phase 2 portion treatment emergent AEs will be summarized by treatment group. Treatment-emergent is defined as all events starting during or after the first dose of study drug (or axitinib) until 28 days following the last dose of study drug or axitinib, whichever is later. The number and percentage of patients with AEs will be displayed by SOC and PT. Summaries will be provided of AEs by grade and of AEs by relationship to study medication. Serious AEs, AEs leading to study discontinuation, AEs resulting in dose delay, and AEs with an outcome of death will be summarized and listed.

For the phase 1b portion, a summary table and listing will also be provided for DLTs.

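### Because treatment-emergent status rests on start date alone and a fall in grade opens a new AE record, an improving baseline AE of grade 2 or higher can be tabulated as treatment-emergent

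*Protocol*

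**What the plan says.** Four rules meet on this point.

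- **Recording a grade change.** Protocol 8.3.9: "Any increase or decrease in adverse event grade should be recorded as a new adverse event". It does not distinguish events that began before dosing from those that began after.
- **Events before dosing.** Protocol 8.3.2: "Adverse events occurring prior to the initiation of the study treatment will be considered" baseline-emergent AEs, kept on their own forms. The footnotes to the Phase 2 schedules (Protocol Tables 9 to 11) send events from first dose onward to the AE form.
- **Treatment-emergent status.** SAP 12.2, in the same terms as Protocol 10.5.2: "All AEs with an onset after initiation of treatment will be considered as treatment-emergent AEs". SAP 12.2 then restates the definition with an end to the window: "all events starting during or after the first dose of study drug (or axitinib) until 28 days following the last dose".
- **Preexisting conditions.** Directly after the onset rule, both documents add: "A preexisting condition that worsens during the treatment period will also be considered as a treatment emergent AE".

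For reporting, SAP 12.2 counts patients by system organ class and preferred term and compares categorical safety values between arms by chi-square or Fisher test. Phase 2 Table 14.3.1.4 (SAP 19.4) uses each patient's maximum CTCAE grade. The Phase 2 in-text AE tables (SAP 19.3) are by grade and do not say maximum.

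**The concern.** The start-date test and the grade-change rule do not fit together. The first assumes that a start date after first dose means something new has happened to the patient. The second creates such a start date when an existing event gets milder. No sentence in either document compares a record with the grade at entry, links grade-change records to one episode, or drops records that show only improvement.

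The frequency and severity of AEs is a Phase 2 secondary objective. A patient whose baseline problem eased could be counted as having an AE that arose on treatment, with an investigator judgement of relatedness attached. Such records can occur in both arms, so they would add background to the any-grade rates that the chi-square or Fisher tests compare.

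**Working it through.** The plan states no figure on this point, so the check is a trace of the rules.

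**Inputs.** Protocol 8.3.9 (recording), 8.3.2 (baseline-emergent class), 8.2.1 (AE definition) and 10.5.2 (treatment-emergent rule); SAP 12.2 (treatment-emergent rule and patient-level counts); SAP 19.3 and 19.4 (Phase 2 tables).

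**Trace.**

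| Course of event | Record under 8.3.9 | Status under SAP 12.2 | Effect on tables |
|---|---|---|---|
| Baseline-emergent, grade 2 falls to 1 after first dose | New grade 1 record, post-dose start | Treatment-emergent by start date; not by the worsening sentence | Patient added to that term at grade 1 if no other treatment-emergent record exists for it |
| Baseline-emergent, grade 3 falls to 2 | New grade 2 record, post-dose start | Same conflict | Patient added at grade 2 |
| Baseline-emergent, grade 1 resolves | A resolution; not clearly a new AE | None clearly | None clearly |
| Symptom held only as medical history | Rule speaks of AE grade; not clearly a new AE | None clearly | None clearly |
| On-study event, grade 3 to 2 to 1 | Three records | All treatment-emergent | One patient per term; grade 3 in Table 14.3.1.4; placement in the in-text by-grade tables not stated |

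**Which grades are reachable.** Let g be the grade at entry and h the grade of the new record. An improvement that is not a resolution needs 1 ≤ h ≤ g − 1.

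- Hence g must be at least 2.
- A spurious grade 3 record (h = 3) needs a grade 4 event at entry.
- A grade 2 entry event can yield only a grade 1 record.

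**Direction.** Let p1 and p0 be the true any-grade proportions in the two arms. Let f be the share of otherwise event-free patients who gain only an improvement record, assumed equal in both arms.

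- Tabulated proportion = p + f(1 − p).
- Tabulated difference = [p1 + f(1 − p1)] − [p0 + f(1 − p0)] = (p1 − p0)(1 − f).

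For purely assumed f of 3%, 6% and 10%, the difference keeps 97%, 94% and 90% of its size. The documents give no value for f. Improvement on treatment could also differ by arm, in which case the direction is not fixed. These figures illustrate the formula and do not estimate the effect in this trial.

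**The case against.** The best defence is intent. The worsening sentence would be unnecessary if an unworsened preexisting condition already counted. Protocol 8.2.1 treats an AE as something untoward and lists "All possibly related and unrelated illnesses, including the worsening of a preexisting illness"; improvement is not untoward. Pre-dose events also sit on a separate form and are listed with the baseline data (SAP Listing 16.2.4.8). All of this stands as evidence of what was meant. It does not settle the matter, because the worsening sentence is worded as an addition to the onset rule and so excludes nothing. Separate forms do not remove the new record either.

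The defence also narrows the problem, and these points stand:

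- Protocol 5.1.1 requires "Resolution of all acute adverse events resulting from prior cancer therapies to NCI CTCAE grade ≤ 1 or baseline (except alopecia"), so residual toxicity from prior therapy is mostly grade 1 at entry and cannot trigger the mechanism. What remains is the baseline exception in that criterion and conditions not caused by prior therapy.
- Haemoglobin down to 9.0 g/dL is allowed at entry, but a low value is recorded as an AE only if clinically significant (Protocol 8.1.1).
- Counting patients by term, with maximum grade in Table 14.3.1.4, already stops a fluctuating on-study event from being counted several times there.

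A reader might infer that the rule blurs the anaemia signal, TRC105's dose-limiting toxicity, for example by adding false events to the 47% anaemia rate at 10 mg/kg in the bevacizumab study (Protocol 2.3.2.1). The documents do not support that. That rate is nine of 19 patients, three at grade 2 and six at grade 3, and an entry grade 2 event that improves gives a grade 1 record, which does not belong in it. Dose-limiting anaemia is grade 3 or higher (Protocol Table 6).

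**Conclusion.** The defect holds in limited form. As written, the rules allow a baseline-emergent AE of grade 2 or higher that falls to a lower, non-zero grade to be flagged treatment-emergent, against the evident purpose of the adjacent worsening sentence. The conflict should be settled before the safety tables are programmed.

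The effect lies mainly in any-grade incidence, mostly at grade 1, and in the between-arm tests on it. Grade 3-4 counts are essentially unaffected. Its size is unknown, since the documents give no frequency of graded AEs at entry and no rate of partial improvement. The conclusion assumes that sites follow 8.3.9 literally for events that began before first dose.

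It would go too far to conclude that every baseline symptom that improves is tabulated as new toxicity. Events that resolve completely, grade 1 entry events and symptoms held only as medical history do not clearly produce a new AE record.

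**What to change.** 1. In SAP 12.2, keep the window from first dose to 28 days after last dose. Add that a record is treatment-emergent only if no event of the same preferred term was ongoing at first dose, or if its grade exceeds the highest grade of that term ongoing at first dose. This turns the worsening sentence into an operative test. Since Protocol 10.5.2 uses onset alone, note the refinement in SAP section 15.
2. Apply the per-patient maximum-grade rule of Table 14.3.1.4 to the in-text by-grade tables in SAP 19.3.
3. Confirm that the baseline-emergent AE form captures grade. SAP section 7 shows that it holds start and stop dates; neither document says whether it holds grade.
4. Leave Protocol 8.3.9 unchanged. Separate records at each grade change preserve the time spent at each grade. Changing the rule would need a protocol amendment and, during enrolment, would leave AE data collected under two conventions.

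The cost is a programming rule and slightly lower any-grade counts. Those lower counts include leaving out a recurrence at or below the entry grade when the event was ongoing at first dose. If grade proves not to be on the baseline form, the comparison will need another source for it.
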